In Part 2, (expansion), patients will be assigned to the recommended dose level(s) and schedule(s) of ADCT-402 identified in Part 1 based on evolving safety, efficacy and pharmacokinetic data.

The *population* in Part 2 expansion may be restricted to specific histologies based on both signals of activity and the safety observed in Part 1.

Further, *dose levels and schedules* evaluated in Part 2 may include but are not limited to the following:

- A. **90, 120, 150, and/or 200 µg/kg:** Dosing every 3 weeks.
- B. **120 µg/kg:** Dosing every 3 weeks for 2 cycles. Patients with at least SD after the second cycle continue treatment at a reduced dose of 60 µg/kg q6weeks, beginning 6 weeks after Cycle 2 infusion.
- C. **150 µg/kg:** Dosing every 3 weeks for 2 cycles. Patients with at least SD after the second cycle continue treatment at a reduced dose of 60 µg/kg q6weeks, beginning 6 weeks after Cycle 2 infusion.
- D. **200 µg/kg:** Dosing every 6 weeks for 2 cycles. For patients with at least SD 6 weeks after Cycle 2, continue treatment at a reduced dose of 60 µg/kg q6weeks, beginning 6 weeks after Cycle 2 infusion.
- E. **200 µg/kg:** Dosing every 6 weeks. For patients with at least SD 6 weeks after Cycle 1, continue treatment at a reduced dose of 60 µg/kg every 6 weeks beginning 6 weeks after Cycle 1 infusion.

The continuation of each patient's treatment will be based on an independent verification of local response assessments, unless otherwise approved by the sponsor.

The DESC will determine and document the dose levels, schedules, and disease subtypes to be evaluated in Part 2. These determinations by the DESC will be provided in writing.

Based on emerging safety and efficacy profile, the DESC may add additional cohorts to part 2 of the study with the same or different dosing regimens and for the same or different B-cell NHL histologies. The dose will not exceed the highest dose tested in part 1 at which 3 patients cleared the DLT observation period.

Patients who discontinue treatment for any reason other than disease progression will continue to be followed approximately every 12 weeks from the last disease assessment until disease progression, or initiation of new anticancer treatment.

After documentation of disease progression or start of new treatment, patients will be followed (by telephone contact or chart review) approximately every 12 weeks for up to 12 months after the last dose of study drug to collect survival information.

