During Part 1, the DESC may expand enrollment at any dose level in which 3 patients have completed the DLT observation period if at least 1 patient in the study has achieved a partial response (PR, [Section 6.1](#)) or better, or if further evaluation of PK or PD data is deemed necessary to characterize pharmacology in humans. No more than 10 patients in total can be treated at any dose level unless ≥ 3 of the 10 patients have achieved a PR or better.

During dose expansion (part 2), patients will be monitored for safety using the same DLT criteria employed during dose-escalation. If during the treatment period, > 30% of patients experience safety events that would meet the criteria that define a DLT in the dose-escalation phase of the study, enrollment in the expansion cohort(s) may be paused and the study data reviewed to determine whether additional monitoring or other action (such as alternate dose levels) should be evaluated prior to further enrollment.

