## **4 Statistical methods**

All analyses use SAS® version 9.4 or higher. Summary tables will be organized by each dose level; if some dose levels have few patients, then dose levels could be combined into dose ranges. All available data will be used in the analyses, and important data will be included in data listings, sorted by dose level, patient, and by visit within patient. Missing data will not be imputed, except via censoring in survival analyses and as otherwise specified.

Unless otherwise noted, categorical data will be presented using counts and percentages, with the number of patients in the analysis set by treatment group as the denominator for percentages. Percentages will be rounded to one decimal place, except 100% will be displayed without any decimal places and percentages will not be displayed for zero counts. Continuous data, unless otherwise noted, will be summarized using the number of observations (n), mean, standard deviation (std), median, minimum, and maximum. Minima and maxima will be rounded to the precision of the original value, and means, medians, and 95% confidence intervals (CIs) if presented will be rounded to 1 decimal place greater than the precision of the original value. The std will be rounded to 2 decimal places greater than the precision of the original value, up to a maximum of 3 decimal places.

No hypothesis testing will be performed in this study.

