#### **4.1.3 Efficacy Analysis Set**

The efficacy analysis set consists of patients who receive at least one dose of ADCT-402 with a valid baseline and at least one valid post-baseline disease assessment or patients who have documented progression of disease or death at any time after the first dose of study drug and before the start of any subsequent anticancer therapy or procedure.

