### 4.9.1 Overall Response Rate

Overall response rate is defined as the proportion of patients who achieve either CR or PR as best overall response as assessed by investigators according to the Lugano Classification criteria before the start of subsequent anticancer therapy or procedure.

The order of overall response category is: CR, PR, SD, NE, PD (including disease recurrence/relapse). The overall response category will be derived based on response assessment performed on or before the start of subsequent anticancer therapy/procedure. Patients without documented subsequent anticancer therapy and/or with missing start date of anticancer therapy will be considered as not having received subsequent anticancer therapy. If a patient only has one valid disease assessment which is SD, and the assessment is within 35 days after the first dose, the overall response for this patient will be considered as NE.

The overall response rate and the corresponding 95% two-sided exact confidence interval at each dose level will be presented. Subgroup analysis may be provided for disease subtype, disease stage, double/triple hit (yes/no), bulky disease (yes/no), age group, sex, country, response to the first line and/or most recent line of prior systematic therapy (relapse: CR+PR vs. refractory: SD+PD vs. other: NE + missing), and other relevant variables.

Percent change from baseline in the sum of product of diameters (SPD) for target lesions will be presented for available data in the efficacy analysis set by dose level. These data will also be displayed as a waterfall plot, with vertical bars representing the sorted values of best percent reduction for each patient.

Tumor response and lesion measurement will be listed by assessment visit.

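### For a dose level expanded past 10 patients in Part 1 under the 3-of-10 response rule, the by-dose-level ORR includes the patients who triggered the expansion and is biased upward, conditional on expansion

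*SAP*

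**What the plan says.** - Protocol 3.2, in a paragraph about Part 1 and repeated in SAP 3, limits the size of a level: "No more than 10 patients in total can be treated at any dose level unless ≥ 3 of the 10 patients" have a PR or better.
- The same paragraph lets the Dose Escalation Steering Committee (DESC) enlarge a level once 3 patients have completed the DLT period, "if at least 1 patient in the study has achieved a partial response" or better, or if PK or PD data call for it. That condition is not specific to the level.
- Protocol 3.1 bases the Part 2 doses and schedules partly on Part 1 efficacy. It adds that the Part 2 population "may be restricted to specific histologies based on both signals of activity and the safety observed in Part 1".
- SAP 4.9.1 gives the reporting rule: "The overall response rate and the corresponding 95% two-sided exact confidence interval at each dose level will be presented". SAP 4 adds "Summary tables will be organized by each dose level" and "All available data will be used in the analyses".
- The efficacy analysis set (SAP 4.1.3) is defined by dosing and disease assessment. It does not separate Part 1 from Part 2, or the first 10 patients at a level from later ones.
- SAP 4.9.1 lists optional ORR subgroups. Neither Part nor position relative to the 3-of-10 decision is named, although the list ends with an open category of other variables.

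**The concern.** The 3-of-10 rule is a response-based continuation rule. A level that passes 10 patients under it does so because its first 10 did well enough, so those 10 are a favourable sample given that expansion took place. If they are then counted with later patients in one ORR for the level, the data that triggered the expansion are used again to estimate activity there. The reported rate at expanded levels is too high on average, and the excess is largest when the drug is least active.

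A milder form of the same problem arises if Part 1 patients at a dose chosen partly for its efficacy are tabulated together with Part 2 patients at that dose. The Part 2 options in Protocol 3.1 repeat Part 1 doses, so a by-dose table can mix the two. Neither document mentions the selection or adjusts for it.

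**Working it through.** **Inputs.** From the documents: a first look at 10 patients, with expansion if at least 3 respond (Protocol 3.2, SAP 3), and ORR as a simple proportion with an exact 95% interval per level (SAP 4.9.1), read here as Clopper-Pearson. The documents give no target ORR, no operating characteristics for the rule and no final size per level, so there is no derived figure to reproduce. True ORR p and final size N are therefore assumptions, shown over a range. One binomial rate per level is also assumed.

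**Formulas.** Let X be the responders among the first 10, X ~ Bin(10, p).

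- Probability of expansion: P(X ≥ 3).
- Expected pooled ORR given expansion: (E[X | X ≥ 3] + (N − 10)p) / N.
- Expected ORR at a level that stops at 10: E[X | X ≤ 2] / 10.

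**Worked case, p = 0.20, N = 20.**

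1. P(X = 0, 1, 2) = 0.1074, 0.2684, 0.3020, which sum to 0.6778. So P(X ≥ 3) = 0.3222.
2. The contribution to E[X] from X ≤ 2 is 0.2684 + 2 × 0.3020 = 0.8724. E[X] = 2, so the part from X ≥ 3 is 1.1276, and E[X | X ≥ 3] = 1.1276 / 0.3222 = 3.50. The first 10 at an expanded level are expected to show 35.0%.
3. Pooled ORR: (3.50 + 10 × 0.20) / 20 = 27.5%, a bias of +7.5 points.
4. Stopped levels: 0.8724 / 0.6778 / 10 = 12.9%.
5. Average over both outcomes: 0.3222 × 27.5% + 0.6778 × 12.9% = 17.6%, which is 2.4 points low.

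**Range.** Exact enumeration gives:

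| True ORR | P(expand) | First 10, if expanded | Pooled ORR, N = 20 (bias) | Bias, N = 30 | Bias, N = 60 | Coverage, N = 20 | Stopped at 10 |
|---|---|---|---|---|---|---|---|
| 10% | 7.0% | 32.1% | 21.0% (+11.0) | +7.4 | +3.7 | 88.5% | 8.3% |
| 20% | 32.2% | 35.0% | 27.5% (+7.5) | +5.0 | +2.5 | 97.0% | 12.9% |
| 30% | 61.7% | 39.1% | 34.5% (+4.5) | +3.0 | +1.5 | 97.2% | 15.4% |
| 40% | 83.3% | 44.6% | 42.3% (+2.3) | +1.5 | +0.8 | 97.3% | 16.9% |
| 50% | 94.5% | 51.9% | 50.9% (+0.9) | +0.6 | +0.3 | 96.9% | 17.9% |

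Biases are in percentage points. Coverage is that of the pooled exact 95% interval, given expansion. At a true 10% and N = 20, every miss lies above the truth (11.5%). Coverage is 89.6% at a true 15% and N = 20. At N = 15 it is 84.5%, 91.0% and 94.4% at a true 10, 15 and 20%.

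**After the split.** Patients enrolled after the decision have expected ORR equal to p, so the 3-of-10 rule causes no bias in them. The price is precision: at 20% observed, the exact interval is 2.5–55.6% for 2/10 and 5.7–43.7% for 4/20.

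**The case against.** Several points on the other side stand and limit the finding.

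- **Scope of the rule.** A reader might infer that every level above 10 patients got there through 3 of 10 responses. The cap is written for Part 1. Part 2 cohorts of about 10 to 20 (Protocol 7.3) are set by the DESC, and nothing says the cap binds them. The figures above do not describe a level that passes 10 only through Part 2.
- **Pooling.** A reader might infer that the SAP expressly combines the Parts. No sentence says so. Pooling follows from the by-dose layout, the use of all data and the absence of a committed split. The open subgroup category permits a split but does not promise one, and SAP 4 also lets sparse levels be merged into dose ranges.
- **Direction.** The bias is conditional on expansion. Levels stopped at 10 err low, and the average over all levels is slightly low. The plan reports every level.
- **Role of ORR.** A reader might infer that ORR is the main measure for choosing dose. It is one of four secondary activity measures. Part 2 choices also rest on safety and PK, and the DESC works from emerging data rather than from this final table. There is no hypothesis testing, so type I error is not at issue.
- **Interval performance.** With N = 20, coverage is about 97% at a true ORR of 20% or more. At a true 10%, expansion followed by an interval that misses the truth occurs for about 0.07 × 0.115 = 0.8% of levels.
- **One rate per level.** A level can contain several schedules (Protocol 3.1) and up to seven histologies (Protocol 3.3.1). If Part 2 is restricted to more responsive histologies, the true rate changes; that is a different population, not estimation bias.

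A reader might also reach for a two-stage unbiased estimator. It needs a fixed stage rule and a second-stage size that does not depend on the data. Here the number and make-up of cohorts are DESC decisions that take observed safety and efficacy into account (Protocol 7.3), so it does not fit.

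None of this removes the bias at a level expanded under the rule. Low estimates at stopped levels do not correct the high ones at expanded levels, and each level has its own row.

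**Conclusion.** The point holds for levels expanded past 10 in Part 1 under the 3-of-10 rule, and only conditionally on that expansion. It rests on an assumed true ORR, an assumed final n, one response rate per level, and a reading of the SAP as pooling by dose. The bias matters at a true ORR of 10 to 30% with small final numbers, and is negligible at 50% or more. Interval coverage is a concern only at low true ORR. For levels enlarged only through Part 2, selection on Part 1 efficacy pushes the same way, but the documents give no basis for a figure. This is a minor estimation and reporting issue on a descriptive secondary endpoint.

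**What to change.** In SAP 4.9.1, present ORR with its exact 95% interval by Part within dose level. For any level expanded past 10 in Part 1, add a row for patients enrolled after the 3-of-10 decision. Keep the pooled figure beside these rows, with a note that it includes the patients whose responses were used for selection. Part 2 alone leaves out the Part 1 data used for selection, but later Part 2 cohorts may themselves be chosen on emerging data, and the note should say so.

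The cost is a few extra table rows and wider intervals for the split estimates, as the 2/10 and 4/20 example shows. For that reason the split rows are proposed alongside the pooled figure and not in its place. Data collection and study conduct do not change.

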### 4.9.2 Duration of Response

Duration of response will be defined for patients with CR or PR only as the interval between the date of initial documentation of a response and the date of first documented evidence of progressive disease (based on radiographic or clinical progression at EOT/end of study [EOS]) or death. Patients who had the event after the start of subsequent anticancer therapy/procedure, or are progression-free and alive at the time of clinical cut-off, or have unknown status, will be censored at the last valid tumor assessment on or before the start of subsequent anticancer therapy/procedure or clinical cut-off time. When a subsequent anticancer therapy is used and progressive disease (based on radiographic or clinical progression at EOT/EOS) is observed within 6 days, they will be considered as the same visit (within the +/-6 days visit window) and the patient will be counted as having an event (losing the response).

Duration of response will be estimated and displayed by dose levels for the efficacy analysis set using Kaplan-Meier methods (SAS® PROC LIFETEST). A Kaplan-Meier plot will be presented.

Subgroup analyses may be provided for disease subtype, disease stage, double/triple hit (yes/no), bulky disease (yes/no), age group, response to the first line and/or most recent line of prior systematic therapy (relapse: CR+PR vs. refractory: SD+PD vs. other: NE + missing), best response to ADCT-402 (CR/PR), and other relevant variables.

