6.1 Efficacy Assessments

Disease assessments will occur every other cycle for the first 2 evaluations (6 weeks [end of Cycle 2 \pm 1 week] and 12 weeks [end of Cycle 4 \pm 1 week]), and every third cycle (every 9 weeks [e.g., end of Cycles 7, 10, 13, etc., \pm 1 week]) thereafter until progression, or more frequently, if clinically indicated.

Patients Initially Treated Every 3 weeks

- To be conducted within 6 days prior to Day 1 of Cycles 3 and 5 and thereafter every third cycle (i.e., Cycles 8, 11, 14, etc.), until disease progression, or more frequently, if clinically indicated.

Patients who initially follow a three week dose schedule and then transition to a six week schedule following cycle 2 should have disease assessments ~6 weeks after Cycle 1 Day 1, ~12 weeks after Cycle 1 Day 1, and thereafter at least every 12 weeks.

Patients Initially Treated Every 6 weeks

- For patients who have reduced dosing frequency and are following a 6 week schedule, disease assessments should occur approximately 6 weeks and 12 weeks after Cycle 1 Day 1, and thereafter at least every 12 weeks. It is understood that there will be a \pm 6 day window for restaging of these patients.

For patients in Part 2: Treatment continuation will require independent verification of the local response assessment unless otherwise approved by the sponsor.

Assessments may be performed within \pm 1 week of the required timepoint and response assessment must be available prior to initiation of dosing at the subsequent cycle.

In case of dose delays, disease assessment should be maintained at the frequencies defined above and response assessment is required prior to resumption of ADCT-402 dosing (only if the interval from last scan is \geq 6/9/12 weeks, as applicable) to rule out disease progression.

The patient's response to treatment will be determined by the Investigator as complete response (CR), partial response (PR), stable disease (SD), or progressive disease (PD), based on the 2014 Lugano Classification Criteria ([Appendix 12.2](#)). Images will be obtained according to local site imaging requirements and may be required to be submitted for a central/independent review. Submission instructions for the central/independent review will be provided in a separate manual.

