7.6.2.2 Duration of Response

Duration of response will be defined among responders (CR or PR) as the time from the earliest date of first response until the first date of either disease progression or death due to any cause. The date of disease progression will be defined as the earliest date of disease progression as assessed by the Investigator using the 2014 Lugano Classification for response ([Appendix 12.2](#)). For patients who have not progressed or died at the time of the analysis, censoring will be performed using the date of the last valid disease assessment. In addition, patients with disease progression or death after an extended loss to follow-up will be censored at the date of the last valid disease assessment prior to the extended loss to follow-up. The data will be analyzed by Kaplan-Meier method. The median duration of response and 95% CI will be presented. Further details will be outlined in the SAP.

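### The optional split of duration of response by best response (CR/PR) starts the clock at first response, so time spent waiting to convert from PR to CR is credited to the CR group

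*SAP*

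**What the plan says.** SAP 4.9.2 defines DOR, for patients with CR or PR, as "the interval between the date of initial documentation of a response and the date of first documented evidence of progressive disease" or death. Protocol 7.6.2.2 uses the same starting point: "time from the earliest date of first response until the first date of either disease progression or death due to any cause".

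The method in SAP 4.9.2 is Kaplan-Meier: "Duration of response will be estimated and displayed by dose levels for the efficacy analysis set using Kaplan-Meier methods". The section then gives an optional list that opens "Subgroup analyses may be provided for disease subtype, disease stage" and includes "best response to ADCT-402 (CR/PR"). The other factors named there (subtype, stage, double/triple hit, bulky disease, age group, response to prior therapy) are all known before treatment starts.

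SAP 4.9.1 settles how best response is reached. The ranking is "The order of overall response category is: CR, PR, SD, NE, PD", and the category is "derived based on response assessment performed on or before the start of subsequent anticancer therapy/procedure". A later CR therefore overrides an earlier PR.

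Neither document gives a landmark, a time-dependent method, a duration-of-CR endpoint or a caution on reading this split. SAP section 4 states that the study tests no hypotheses.

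**The concern.** The grouping variable is not known when the DOR clock starts. A patient whose first documented response is PR is counted as CR only after remaining in response until a later scan shows CR, and all of that waiting time enters the CR curve. A patient in PR who progresses, dies or is censored before converting stays in the PR curve. This is guarantee-time (immortal-time) bias. It lengthens the CR curve and shortens the PR curve whether or not depth of response affects durability.

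What is at stake is the reading of one table or plot. The medians and curves could be taken as evidence that CR brings longer responses when part or all of the gap comes from the construction. The absence of a p-value does not prevent that reading.

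**Working it through.** The plan states no expected DOR, CR share or conversion rate, so there is no figure of its own to reproduce. The check asks what the planned split shows when CR has no effect at all.

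**Scan times, from Protocol 6.1.** With dosing every 3 weeks, assessments fall "within 6 days prior to Day 1 of Cycles 3 and 5 and thereafter every third cycle", which is about weeks 6, 12 and 21. Measured from a first response at week 6, the next two scans come at 12 − 6 = 6 weeks (t1 = 1.4 months) and 21 − 6 = 15 weeks (t2 = 3.5 months). A patient who converts at week 12 has 6 guaranteed weeks in response. The next scheduled scan that can show progression is 15 weeks after first response. On the 6-week schedule, with later scans at the longest allowed interval of 12 weeks, it is 24 − 6 = 18 weeks.

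**Assumptions not in the documents.** True DOR is exponential with median m and the same for everyone, and progression is observed exactly. There is no censoring. A share p = 0.30 is in CR at first response. Each PR patient still in response converts with probability c = 0.2 to 0.4 at t1 and again at t2.

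**Formulas.** Let S(t) = exp(−t·ln2/m) and k = c·S(t1) + (1 − c)·c·S(t2), the fraction of initial PR patients who convert.
- CR share: A = p + (1 − p)·k.
- CR median, if beyond t2: S(t) = 0.5·A / [p + (1 − p)(1 − (1 − c)²)].
- PR median, if beyond t2: S(t) = 0.5·(1 − k) / (1 − c)².
- PR median, if between t1 and t2: S(t) = [0.5·(1 − k) + (1 − c)·c·S(t2)] / (1 − c).

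**m = 5 months:** S(t1) = 0.8236, S(t2) = 0.6156.
- c = 0.2: k = 0.1647 + 0.0985 = 0.2632; A = 0.3 + 0.7 × 0.2632 = 0.4842. CR: S = 0.2421/0.552 = 0.4386, median 5.9. PR: S = 0.3684/0.64 = 0.5756, median 4.0.
- c = 0.4: k = 0.3294 + 0.1477 = 0.4772; A = 0.6340. CR: S = 0.3170/0.748 = 0.4238, median 6.2. PR: S = (0.2614 + 0.1477)/0.6 = 0.6819, median 2.8.

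**m = 8 months:** S(t1) = 0.8858, S(t2) = 0.7384.
- c = 0.2: k = 0.2953, A = 0.5067. CR: S = 0.2534/0.552 = 0.4590, median 9.0. PR: S = 0.3524/0.64 = 0.5506, median 6.9.
- c = 0.4: k = 0.5315, A = 0.6721. CR: S = 0.3360/0.748 = 0.4493, median 9.2. PR: S = 0.2342/0.36 = 0.6506, median 5.0.

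Simulation of 400,000 responders per scenario agrees to rounding.

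**Sensitivity to the CR share at first response (m = 5, c = 0.2).** The PR median stays at 4.0, because p cancels from its formula. With p = 0, CR: S = 0.1316/0.36 = 0.3656, median 7.3. With p = 0.5, A = 0.5 + 0.5 × 0.2632 = 0.6316 and CR: S = 0.3158/0.68 = 0.4644, median 5.5. The bias shrinks as more patients are in CR from the start, because those patients carry no guaranteed time.

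**A second set of assumptions.** Here conversion was possible at every later scan with probability 15% or 30%, the CR share at first response was 0% to 50%, and both scan schedules were used. A true median of 26 weeks for everyone appeared as 32 to 52 weeks for CR and 11 to 17 weeks for PR.

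**Does a landmark remove it?** Among patients still in response at t1, grouped by CR status at t1 and timed from t1, simulated medians were about 5 months in both groups (true 5) and about 8 months in both (true 8). A week-12 landmark under the second set gave about 26 weeks in both groups.

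**The case against.** The strongest case against making much of this is that the analysis is optional and descriptive, concerns a secondary endpoint in a phase 1 study, and may never be produced. The planned DOR display is by dose level. Response by visit and derived DOR are both listed (SAP 4.9 and 4.9.1), so a landmark version could be built later. All of this stands. It limits the weight of the point, but it does not make the split unbiased if it is shown.

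A reader might infer more than the documents support:
- *That every CR patient must have a longer DOR.* Converters have a guaranteed minimum only. Under the main assumptions above, a converter's DOR is shorter than that of a randomly drawn PR patient in 27% to 38% of pairs.
- *That early progressors can only be in the PR group.* Patients in CR at first response can progress at any time and still count as CR. With p = 0.30, about 30% of those who progress before the first conversion scan are in the CR group.
- *That the medians above predict this trial's results.* They rest on inputs that neither document gives. Real data will also have progression found mostly at scheduled scans and censoring at subsequent therapy.
- *That the sponsor intends to argue benefit from this contrast.* Neither document plans such a use.

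**Conclusion.** The point holds as a minor, inexpensive improvement. As written, SAP 4.9.2 allows a CR/PR split of DOR that favours CR at group level even when CR has no effect on durability, through the waiting time of PR-to-CR converters. The direction follows from the definitions in SAP 4.9.1 and 4.9.2. The size does not: under the assumed inputs, the CR median is 0.9 to 1.2 months above the true value. The PR median is 1.0 to 2.2 months below it at a true median of 5 months, and 1.1 to 3.0 months below it at 8 months, so most of the gap usually lies on the PR side. The size varies with the conversion rate and with the share already in CR at first response. Overall DOR, ORR, PFS, OS and MTD determination are not touched.

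**What to change.** Add one sentence to SAP 4.9.2: any CR/PR split of DOR will group patients by response status at a fixed landmark (for example the 12-week assessment, which the 3-week and 6-week schedules share), among those still in response at that point, with time counted from the landmark. Duration of CR from the first CR date may be reported as a separate description, but not as a CR-versus-PR comparison.

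The cost falls on that subgroup table alone. Patients who progress or are censored before the landmark drop out of it. So do those who first respond after it, at about week 21 or week 24 onward. Conversions after the landmark count as PR. Protocol 7.3 plans Part 2 cohorts of about 10 to 20, so the table may need pooling across cohorts. The main DOR analysis stays as it is.
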